Paradata, defined as auxiliary data that capture details about the *process* of interaction with the technology, will drive our understanding of user engagement with the mLab App and of subsequent behavior change. Outcomes from HIV prevention and care studies delivered via a mHealth platform have primarily relied on analyses by group assignment and assume that participants' engagement is equitable within the intervention arm and stable for the duration of the trial. The use of paradata in technology interventions involving HIV prevention and care is an understudied area of interest.⁸⁵ While a number of technology-based HIV interventions have previously suggested that online behavioral interventions are acceptable and efficacious in promoting behavioral change,⁸⁶ a recent review of this literature identified very limited reports of participant engagement, measured through paradata, with a technology-based intervention.⁸⁷ In our own recently published work on the effect of a mHealth app for improving symptom burden in PLWH, we monitored app usage throughout the trial and reported this as part of the final outcomes of our study.⁸⁸ Given our prior work, we will examine paradata since this provides an opportunity to monitor and analyze aspects of the mLab App that may play a role in changes in HIV testing rates and linkage to care. By monitoring and analyzing paradata, components of the mLab App, such as the timing, location, and frequency of the rapid images of HIV tests taken by a user and access to other prevention information, will be instrumental in understanding what components of the intervention mediate behavior change. Engagement with the mLab App will furnish a greater understanding of user satisfaction and retention of our intervention. mLab App paradata will have implications for the scale-up and dissemination of this intervention as well as for the development of future technology-based HIV interventions with targeted behavioral outcomes.

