4) To understand high-risk YMSM and YTGW's plans for using the mLab App, barriers to use, and feasibility of using the imaging algorithm (the mLab), Drs. [name] and [name] conducted a mixed methods observational study among 18 YMSM and YTGW (mean age 24) who have all engaged in high-risk sexual behavior (unprotected anal sex) in the past 3 months. Participants used the mLab App and then completed a follow-up survey and an in-depth interview. Participants completed the Health-ITUES survey and rated the mLab App as *Impact on health* (4.3 out of 5), *Useful* (4.4 out of 5) and *Easy to Use* (4.4 out of 5). We collected paradata as part of our pilot study and collected time stamps, pages accessed, test image, type of Internet browser, operating system, and the smartphone device. This paradata mirrors the data that will be captured in Aim 3 and analyzed alongside our primary outcome data. Following the survey, we conducted in-depth interviews to understand high-risk youth's plans for using the mLab App and barriers to use. All of the participants reported this would be a very useful tool for high-risk youth and thought most youth would want to use the mLab App. They also all indicated they would seek follow-up care if they themselves tested positive and saw the principal advantages of the mLab App as being "convenient and portable" and an enabler for promoting uptake of HIV testing. In particular, youth noted that the mLab would be especially helpful to youth who did not have a close relationship

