Missing Data. Multiple imputation (MI) methods will be applied to address missing values under the missing at random (MAR) assumption (i.e., missingness can be fully accounted for by variables with complete information).¹⁴¹ These analyses will be complemented with assessment of how sensitive the inferences are to the MAR assumptions. Sensitivity analysis will be performed based on selection models for dropout.¹⁴²⁻¹⁴⁴ Intention-to-Treat (ITT) Analysis: All analyses will use the ITT principle,¹⁴⁵ which requires subjects' data to be analyzed as randomized, regardless of whether they used the mLab App or not.

Aim 3: Monitor and analyze paradata to understand the effect of user engagement of the mLab App on improving HIV testing rates and linkage to care.

To understand barriers and/or facilitators of its use, the mLab app will automatically collect paradata for each user interaction throughout the study. This paradata is considered "free" in that it does not require any additional effort from the user.¹⁴⁶ This data will be analyzed for each user, as well as aggregated to understand what component of the intervention lead to behavior change. We will specifically examine who uses the mLab App and how frequently it is used over time.

Methods. We will capitalize on the use of the extant mLab software which is written as a mobile-friendly web application in hypertext markup language (HTML), hypertext preprocessor (PHP), JavaScript, and Python (for computer vision), and integrates with REDCap for backend data storage. On each page of the mLab app, a PHP script logs every user interaction before the page of the application is displayed to the user. Therefore, any event that would refresh or send the user to a new page (e.g., HTML links) initiates an event-driven paradata capture. The PHP script transmits the data to REDCap through the secure REDCap API.

Data Analysis. The primary paradata that will be collected is shown in Table 4. From this data, we will derive the following use data for each session: duration on each page, page progression through the application, time from login to result, number of rapid test pictures previewed before sent for result, and total time prior to logout. We will analyze the data on multiple scales and perspectives: individual-level (i.e. user-level), application-level, page-level, session-level, and how these differ by demographic characteristics, HIV testing history, technology

Table. Paradata Collected for Each mLab Event

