1. Unique Code
2. Page accessed
3. Time stamp
4. Rapid test image
5. Internet browser type
6. Operating system
7. Device

use, and outcomes measures. At the app-level, we will analyze timestamp data including time of day and day of the week that HIV self-testing is performed. We will also analyze the time-to-HIV self-testing result from App login -- a primary indicator of usability. Efficiency is a major construct of the Health-ITUDEM model, the guiding theoretical framework for our study (see Figure 4). Additionally, we will measure the amount in bytes of user data transmitted. Importantly, longitudinal analysis will determine if user-experience changes with repeated use.

The paradata collected from each page will be analyzed to generate a “heatmap” of user-interaction (i.e., the distribution of activity for each link/button). Use of the heatmap will inform user duration on each page of the application user interaction with the HIV prevention content, the contact pages, and the help page. We will explore usability issues with consideration for how many times users accessed help, and what page of the mLab app referred them to the help, implying the need for clarification. Similarly, contact page paradata will be analyzed to determine at what point in the use of the imaging software (the mLab) users initiated contact with the study team and/or the clinic. Specifically, referring pages to the contact page will be analyzed (i.e., do users engage with contact resources only after a diagnosis is provided?). Finally, we will use paradata to understand when users disengage with the mLab app (e.g., logout after received diagnosis, logout prior to diagnosis, session timeout).

Since the mLab App provides an image-based diagnosis of HIV rapid tests, paradata will be used to understand the process of capturing a photograph for analysis. To this end, we will count the number of images previewed prior to submission of a final image for mLab analysis. Within each image, we will perform digital image analysis to determine orientation, luminosity, and major colors within an image – all factors that would indicate successful analysis in mLab. Importantly, this analysis will be used to improve the computer vision algorithm.

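### Aim 3 paradata are captured at page requests, so dwell time is unobserved on the last page of sessions that end without logout, and the link/button heatmap can show only page requests

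*Combined protocol and SAP*

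**What the plan says.** Aim 3, Methods, describes a web application in which, on each page, "a PHP script logs every user interaction before the page of the application is displayed to the user". It follows that "any event that would refresh or send the user to a new page (e.g., HTML links) initiates an event-driven paradata capture". JavaScript is named as part of the software, but no logging in the browser is described.

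Aim 3, Data Analysis, states: "The primary paradata that will be collected is shown in Table 4". The table printed there has seven fields: unique code, page accessed, time stamp, rapid test image, browser type, operating system and device. Preliminary Data, study 4, reports that the pilot captured six of these (all but the unique code) and adds: "This paradata mirrors the data that will be captured in Aim 3".

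From these data the plan derives, per session, "duration on each page, page progression through the application, time from login to result", the number of test pictures previewed, and total time up to logout. It also plans a heatmap, defined as "the distribution of activity for each link/button". On disengagement it says: "we will use paradata to understand when users disengage with the mLab app (e.g., logout after received diagnosis, logout prior to diagnosis, session timeout". It gives no rule for the duration of a page or session that has no logout.

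**The concern.** The capture method and some of the planned measures do not match. A record written when a page is requested shows that the page was opened. It does not show how long the page was read, what was tapped on it, or when the user left.

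The resulting gaps depend on the behaviour under study. The page where a user leaves without logging out is exactly the page with no recorded duration. Aim 3 asks whether users leave before or after seeing a result, and it plans to compare HIV-positive with HIV-negative users. If groups differ in how they leave after a result, recorded dwell time on that page compares selected subsets of each group. The multiple-imputation paragraph under Aim 2 assumes that missingness is explained by fully observed variables, and it does not mention paradata. Events not logged during follow-up cannot be recovered afterwards.

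**Working it through.** Aim 3 has no sample-size or error figure to reproduce. The check sets each planned measure against the capture rule and the listed fields.

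**1. Page duration.** Duration of page *i* = time stamp of request *i*+1 minus time stamp of request *i*. This needs a following request. If the user logs out, and logout loads a page, the last content page has a duration. If the browser is closed or the session times out, it has none.

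**2. Total session time.** The plan defines this up to logout, so it exists for sessions with logout and is undefined for the rest.

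**3. Mean dwell on an exit page.** Let *e* be the share of visits to the page that end there without logout, *m_c* the true mean dwell of users who continued or logged out, and *m_x* that of users who left.
- True mean = (1 − *e*)·*m_c* + *e*·*m_x*
- Observed mean = *m_c*
- Bias = *m_c* − true mean = *e*·(*m_c* − *m_x*)

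The bias is zero if the two groups dwell equally. Otherwise it can go either way. The documents give none of the three quantities.

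**4. Heatmap.** A link that opens a distinct page can be reconstructed from the page sequence. Two links to the same page cannot be separated without an element field. A control that loads no page leaves no record under the described trigger. Possible examples from the Aim 1 use cases are playing a video, starting the timer and saving a fact. The documents do not say which of these reload the page, or whether an image preview does.

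**5. Type of disengagement.** The last page recorded, and whether a logout record exists, can be read from the log. A timeout cannot be told apart from a closed browser.

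**6. Illustration of lost session time.** All inputs are assumptions. Let *q* be the share of sessions ending without a logged event and *f* the share of session time spent on the last page. If sessions with and without logout are equally long on average, the unobserved share of session time is *q*·*f*. With *K* pages of equal dwell, *f* = 1/*K*.

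| Assumed session | *f* | *q* = 25% | *q* = 50% | *q* = 75% | *q* = 100% |
|---|---|---|---|---|---|
| 3 equal pages | 33.3% | 8.3% | 16.7% | 25.0% | 33.3% |
| 5 equal pages | 20.0% | 5.0% | 10.0% | 15.0% | 20.0% |
| 10 equal pages | 10.0% | 2.5% | 5.0% | 7.5% | 10.0% |
| Half the time on last page | 50.0% | 12.5% | 25.0% | 37.5% | 50.0% |

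At *q* = 0 the loss is nil. The table restates the formula and is not evidence of the actual size.

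**The case against.** The strongest reply is that the plan says every user interaction is logged and never says that only page-changing events are. The field list is called primary, not complete, and the app workflow is in attachments that are not available here. This is fair as a caution. However, a script that runs before the page is displayed cannot by itself see what happens afterwards, no other capture is described, and study 4 ties Aim 3 to a near-identical pilot set.

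Four stronger readings are tempting, and the documents do not support them:
- **Last-page time and session length cannot be measured at all.** Sessions with a logged logout give both, and the plan defines total time only up to logout.
- **The location of testing will come out empty.** Location appears once, in the Background paragraph on paradata, within "the timing, location, and frequency of the rapid images of HIV tests taken by a user". No Aim 3 analysis uses it.
- **Bytes transmitted cannot be measured.** There is no listed field, but the amount may be computable from stored data, which include the test image.
- **The engagement results will be biased.** That depends on an unstated logout rate. Equal dwell is also a poor model for test sessions. The window-period item under Protections against Risks requires at least 20 minutes between two screens before an algorithm result is returned. If a user then spends 1 minute on the result page (an assumption), *f* is at most 1/21 = 4.8%, so at most 4.8% of session time is lost even if nobody logs out. This limits the error in session totals. It does not restore dwell time on the result page itself.

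It is also true that Aim 3 covers only arm 1 (N=210) and states no formal hypothesis, and that the primary outcome is self-reported testing.

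**Conclusion.** The concern holds in a limited form. As the capture is described, last-page duration and total session time are unobserved for sessions that end without logout, and the plan expects such sessions. Exit-page dwell time then describes only users who continued or logged out. The heatmap can show page requests, but not in-page actions that load no page, nor which of two links to the same page was used.

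The bias may run from nil to large. Neither its size nor its direction can be set from the documents, which give no logout rate, pages per session or dwell times. The conclusion assumes that no client-side logging exists beyond what is described, and that logout loads a page.

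Page sequence, frequency of use, time of day, help and contact referrals, and login-to-result time (when both pages load in one session) are unaffected, as is the primary outcome. The change is worth making before the trial starts, but it does not threaten the trial's main conclusion.

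**What to change.** **Preferred, before the trial starts.** In Aim 3, Methods, add client-side events in the JavaScript that the app already uses: page hidden or closed, element tapped and image previewed, each with a time stamp and, for taps, an element identifier. Add a flag that separates logout from timeout. The cost is a small programming and retesting task, which fits the app refinement in Aim 1, with possible notice to the IRB and a check that finer logging is covered by the privacy plan. No extra participants or visits are needed.

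**If the logger is not changed.** In Aim 3, Data Analysis, report page and session duration only for sessions with a logged end, give the share without one by subgroup, and label the heatmap as page-request counts. This needs no programming of the app.

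Right-censoring the last page would not repair the existing log on its own. The final record is written as the page loads, so the censored time is zero and carries no information about dwell. Censoring becomes useful only once a later event, such as page hidden, is recorded.

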Heuristic Evaluation with experts, Step 2. End-User Usability Evaluation. Step 3. Review by YAB. Note the Youth Advisory Board members will not be self-testing. They will only review the content and function of the app.

Usability Testing. The goal of the usability evaluation is to refine the mLab App User interface. Usability Testing will promote improving the quality of the user's interaction with and perceptions of the mLab App.

Step 1. Heuristic Evaluation. We will conduct a Heuristic Evaluation with five informaticians who will participate as usability experts and must have training in human-computer interaction and have published in the field of informatics.

Procedures.

Heuristic Evaluators will be asked to complete a short demographic survey. Following completion of the survey, the usability experts will be asked to use the Oraquick test and also the mLab App.

The mLab App is mobile app that is accessible using a login name and password. The app will provide HIV prevention information, push notification reminders for testing, step-by-step instructions for using the OraQuick HIV tests, an image upload function to send an image of your OraQuick HIV test to the study team.

Participants will:

- a) be asked to manually enter the Oraquick test results; and
- b) take a picture of the test results for the app to analyze the results; and
- c) receive the app's interpretation of the Oraquick test results.

By using the app, we are asking participants to help test the app's ability to interpret the results of the OraQuick tests. If you test HIV positive by the OraQuick HIV test and/or the mLab app will provide information on how to set up follow-up confirmatory testing within the following 24 hours. All information within the app will be stored on a secured server at Vanderbilt University.

While Morae Software is recording their actions, participants will be asked to use the following use cases while using the app.

First Login

- 1) Taking A Test
 - a. If it's your first time loggingin, it's time for a test, click on the "New Test" tab
 - i. Watch the video
 - ii. Read the instructions and make sure you are clear on how to complete your OraQuick test
(If you need additional help please click the "Help" tab)
 - iii. Do the Oraquick test
 - iv. Click on the start timer
 - v. Do a task you find relaxing for the duration of the timer
 - vi. Read your results and enter what you think they are
 - vii. Get your results on the results page
- 2) Other tasks:

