- 5) Window Period for Interpretation of Results: In the mLab App, we have added in 2 points of instruction related to the 20-40 minute window period for the Oraquick results – see Appendix L, slides 7 and 11. Second the images will be time stamped and we will not return algorithm results if the time from reporting in screen 7 and the time to take a picture in screen 11 has been less than 20 minutes or more than 40 minutes.
- 6) Invalid Test Results: If the participant reports an invalid result – the software will send the following message back to the study participant: You reported that your results are invalid. An Invalid test result means that there was a problem running the test, either related to the specimen or to the Test Device. An Invalid test will not be interpreted by the mLab App. Repeat the test with a new Divided Pouch and a new oral fluid. Please contact the study team if you are unable to get a valid test result upon repeat testing. If the participant reports an invalid test then we will turn off the ability for the mLab App to return the algorithm results to the participants. However, invalid images will still be stored in REDCap and reviewed by the study team.
- 7) Imaging Algorithm: The parameter values in the mLab App's image processing algorithm have been validated and selected to primarily optimize sensitivity and specificity. However, it is possible for the mLab App to return both false positives and false negatives. The study team will monitor the images that are sent using the mLab App, and will contact study participants in the event of either: 1) the mLab App returns an incorrect result, and 2) a discrepancy between the participant's manually reported result and the mLab App result.

c. Additional Planned Procedures for Protecting Against/Minimizing Potential Risk/Additional Protections for Children

Procedures in the Event of a Reactive HIV Test

In the event a participant has a reactive HIV test, study team members will counsel the participant regarding the meaning of his result. Specifically, the study team will reiterate with the participant that:

- 1) His result is a preliminary positive and it is likely that he is infected with HIV;
- 2) The preliminary positive result needs to be verified with confirmatory testing;
- 3) He needs to return for the results of his confirmatory testing; and
- 4) Resources for counseling and referral to care are available to him.

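### Aim 3's named usability indicator, time from app login to test result, includes the assay wait of at least 20 minutes and should be split into active time and waiting time

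*Combined protocol and SAP*

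**What the plan says.** Aim 3, Data Analysis, derives several quantities for each session, among them "duration on each page, page progression through the application, time from login to result". It then singles one out: "We will also analyze the time-to-HIV self-testing result from App login -- a primary indicator of usability". The next sentence ties it to efficiency, a construct of the study's guiding usability model. The same section plans a longitudinal look at user experience with repeated use, and comparisons by demographic group, device and browser.

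The Aim 1 use cases (Taking A Test) give the order of steps: log in, watch the video, read the instructions, run the test, start the timer, wait, read and enter the result, see the results page. The waiting step reads "Do a task you find relaxing for the duration of the timer".

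Protections against Risks, item 5, refers to "the 20-40 minute window period for the Oraquick results". It makes the app's own reading conditional on an interval between two screens: "we will not return algorithm results if the time from reporting in screen 7 and the time to take a picture in screen 11". The rule works on both sides, below 20 and above 40 minutes. Item 6 withholds the algorithm result when the user reports an invalid test.

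No section says that the wait is removed from the indicator, which result ends the interval, or what value a session without a returned result receives.

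**The concern.** An efficiency measure should get shorter as the user handles the app better. Here a large part of the interval is strip chemistry that no design or experience can shorten. A further part is the user's choice of when to return within the reading window. A real gain in handling is therefore diluted, and a change in return time can look like a change in usability.

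There is also a gap at the end of the interval. If the algorithm result stops the clock, sessions in which it is withheld have no end time, and the plan has no rule for them.

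At stake is what Aim 3 may conclude about efficiency across repeated tests, demographic groups and devices. No trial outcome is affected.

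**Working it through.** The plan gives no expected value, sample-size calculation or test for this indicator, so there is no figure to reproduce.

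**Inputs**
- W, the screen 7-to-screen 11 interval: 20 to 40 minutes whenever an algorithm result is returned (Protections against Risks, item 5).
- A, active minutes outside that interval: not in the documents. Assumed range 5 to 40 minutes.
- Screen 7 is taken as the start of the wait. The screen images are in an appendix that was not available, so this is an assumption.

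**Share of the level.** Indicator = A + W; share of the wait = W / (A + W).

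| A (min) | W = 20 | W = 40 | Range of indicator (min) |
|---|---|---|---|
| 5 | 20/25 = 80% | 40/45 = 89% | 25-45 |
| 10 | 20/30 = 67% | 40/50 = 80% | 30-50 |
| 20 | 20/40 = 50% | 40/60 = 67% | 40-60 |
| 30 | 20/50 = 40% | 40/70 = 57% | 50-70 |
| 40 | 20/60 = 33% | 40/80 = 50% | 60-80 |

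The wait exceeds half of the indicator when A is below 20 minutes (W = 20) or below 40 minutes (W = 40).

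**Dilution.** Suppose active time halves from 10 to 5 minutes while W stays at 20. The indicator falls from 30 to 25, a drop of 5/30 = 17% instead of 50%.

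**Distortion.** A user who photographs the strip at 22 minutes rather than 38 moves the indicator by 16 minutes with no change in handling.

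**Share of the variance.** A constant 20 minutes adds nothing to differences between users; only the spread of W does. With independent parts, share = Var(W) / (Var(W) + Var(A)).
- W uniform on 20-40: Var(W) = 400/12 = 33.3. With SDs of 2 and 1 minutes for the active steps before and after the wait, 33.3/(33.3 + 4 + 1) = 87%. With SDs of 4 and 2, 33.3/(33.3 + 16 + 4) = 63%.
- W with SD 3, as if users return promptly at the timer: 9/(9 + 5) = 64% and 9/(9 + 20) = 31%.
- An illustrative simulation with lognormal active time (medians 5-20 minutes) and lognormal delay beyond 20 minutes (medians 3-10) gave 9% to 53%.

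The answer is set by assumptions and runs from 9% to 87%.

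**Whom the time limit removes.** In the same simulation the limit removed 1% to 25% of sessions, and 3% to 79% of retained sessions lasted more than 40 minutes in total. The slowest tenth on active time were retained 75% to 99% of the time. The slowest tenth on total time were retained 11% to 91% of the time. Two limits apply. Active time and delay were drawn independently, so retention of slow handlers simply follows overall retention. Photographs before 20 minutes, which the rule also excludes, were not simulated.

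**The case against.** The strongest case against is that little is lost. The plan calls this one primary indicator among many. It already derives page durations and page progression, and it analyses help-page use, logout before diagnosis and session timeout. Users who give up are therefore not invisible, and the pieces needed to separate the wait are planned. The longitudinal sentence speaks of user experience in general and does not name this interval. All of that stands and keeps the point small. It does not repair the named indicator, which still contains the wait.

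Three stronger readings are tempting, and the documents do not support them.

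- *A reader might infer that the indicator is cut off at 40 minutes.* The limit applies to screen 7 to screen 11 only. Time before screen 7 (video, instructions) has no stated bound, so the total can exceed 40 minutes.
- *A reader might infer that the slowest or most troubled users are dropped.* The rule is two-sided, and at the upper end it removes late photographers, who need not be slow with the app. It also withholds only the algorithm result. Under Risks Specific to the Use of the mLab App, the manual read is the result of record, and no time limit on it is stated. If the user-entered result stops the clock, the rule truncates nothing.
- *A reader might infer that the indicator mostly measures the test strip, or that group differences mainly reflect waiting.* The first holds only for short active times, which are undocumented. The second depends on the spread of the wait, which is also unknown.

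**Conclusion.** The indicator as written mixes app handling with assay waiting. This holds whichever result ends the interval, because the user-entered result also comes after the timer in the use cases. The 20-minute minimum is enforced only for the algorithm result; for the user-entered result it rests on users following the timer.

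The wait makes up about 80-89% of the level at 5 active minutes, 50-67% at 20 and 33-50% at 40. Its share of between-user variance cannot be settled from the documents.

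The missing end point is conditional. If the algorithm result stops the clock, sessions with a screen 7-to-11 interval under 20 or over 40 minutes, and tests reported invalid, have no value. The end event is made less clear by a contradiction: the description of the app in the Background says participants cannot see its interpretation, while the Arm 1 section says they receive it. These passages must be reconciled.

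Severity is minor: the measure is descriptive, confined to arm 1 (N = 210 in Table 1), with no power calculation or error rate attached.

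**What to change.** 1. Define the start and end events. State whether the user-entered or the algorithm result stops the clock, and reconcile the two passages on whether participants see the app's interpretation.
2. Make active time, net of the screen 7-to-11 wait, the efficiency indicator in the repeat-use and subgroup analyses. If the result-entry page falls between those screens, add its logged duration back, since reading and entering are handling, not waiting.
3. Report the wait and the total time separately.
4. Alongside these, count sessions in which a test was started but no result was returned, by reason: under 20 minutes, over 40 minutes, invalid, timeout, logout.

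Cost: a small amount of extra analysis. Page-level time stamps are already logged, and the app must already compute the screen 7-to-11 interval to apply its own rule, so no new data or visits should be needed. The mapping of logged pages to screens 7 and 11 should be confirmed first.
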